### 3.2.2.1 Eligibility Criteria

### Inclusion criteria

The respondent is 18 years old and above. Mild to moderate score on PHQ-9 ( ≥5 < 10)

 and GAD-7 (≥5 <8) living in the three subdivisions of Petaling District.

# **Exclusion criteria**

- Respondents that have difficulty communicating and understanding the Malay language will be excluded from the study.
- PHQ 9 ≥10 and GAD-7 ≥8 will referred for hospital assessment and will be excluded.
   Suppose the respondent has an unstable severe psychotic mental illness such as
   Schizophrenia, Bipolar and any form of psychotic illness based on DSM- VI diagnostic criteria. This is based on clinical assessment.
- In addition, if the participant were selected but refused to give consent are also excluded from the study

# Withdrawal Criteria

- Respondent could withdraw anytime without being required to give any reason

# 3.2.3 Evaluation: Logic Model

The logic model in **Figure 3.2**, showing the work process of evaluation starting from the output, identification of the target population, activities that are leading to the intervention and outcomes of the intervention.

Problem Statement	Obj: General Improving the	Inputs	Target Population	Activities	Outputs	Outcomes
High prevalence of mental illness among the low socio- economic residents at community Housing Project. Study shown poor knowledge and stigma as barrier to help seeking behaviour Lacking of suitable feasible intervention for the community	health literacy and barrier to achieve good mental health and quality of life Specific -Improve the perception of the susceptibility of illness by improving knowledge mental illness - Reducing barriers to engage in mental health promotion activities	Administrative Resources(3M) Money Manpower materials: Research Phase 1 study identify the Risk Phase 2 Mixed Methods Qualitative study : identification of the barriers and needs by IDI Piloting and Evaluation -Phase 2: Developing a tailor-made psychosocial intervention	Participants who are high risk for mental health illness (mild to moderate scoring on PHQ-9 and GAD-7)	RESHape Modules 6 modules delivered online through RedCap Database Each modules followed by assignment Mindfulness breathing 15 min , 3 to 4 times per week	No. of sessions of the attempts of the modules and the assignment Total scoring of the Assigments	Immediate: Improvement in the mental health Scores(PHQ-9, GAD-7), QOL,(EQ-5D) Resilience FGD: Feedback from participants and community leaders on the interventionIntermediate Improvement of the psychology resilience of the adult parents and youth at the community housing projectLong term Reduction of the national prevalence of mental health issuesImmediate: Improvement of the psychology resilience of the adult parents and youth at the community leaders on the interventionImprovement of the psychology resilience of the adult parents and youth at the community housing project
	Process Evaluation					Outcome Evaluation
Assumptions "Teory of Change" Based on the Health Belief Model: Intervention (Mindfulness and increase in awareness of bariers) improving mental well being by reducing the barriers(negativity) and improving individual self-efficacy.				Internal and Ex Socio-demogra	ternal Factors phic and other psychosocial risk factors	

Figure 3.2: Logic Model for ReSHape Intervention

#### 3.2.3.1 Intervention Group

Respondents selected in the intervention arm will be given the six ReSHape modules over three months, in which each respondent must complete each module and the related assignment (components of the modules were described in detail in table ) in two weeks. The modules will be delivered through REDCap unique link via respondents' email and Whatsapp, in which each link is comprised of the narration of the components of the modules in videos and relevant quizzes. The understanding and the fidelity of the respondents' responses rely on the pre-post quizzes scores and submission of their assignments. Contents of the Self-Help Modules will be based on the cross-cultural elements derived from the mixed methods study output and evidence-based intervention described in the methodology **sub-heading 3.6** (Gillihan, 2020a, 2020b; Howarth et al., 2019; Mathias et al., 2018). Each respondent will be prompted through a reminder on WhatsApp to practice mindful breathing exercises at home. The mechanism of health-related behavioural change is driven by the components from the Health Belief Model **(HBM)**.

#### 3.2.3.2 Control Group

Respondents selected in the control arm will be given a copy of Healthy Mind Modules, Let's TALK pamphlets and an educational video from the Malaysia Ministry of Health (MOH, 2005, 2018). And they will be given the intervention arm module or material at the end of the study **Figure 3.3** 

3.2.3.1a Proses Evaluation

To determine whether programme activities have been implemented as intended. An analytical comparison of planned processes versus actual implementation, determination of strengths and weaknesses of the programme were conducted. Each participant will be monitored with a log from the REDCap online database on the completion of the training sessions and pre-test and post-test scoring of the modules quizzes. The percentage of the execution of tasks, attendance of the training sessions and pre-test and post-test/quizzes scoring of the online modules will be taken as an indicator of the quality and fidelity of the Reshape intervention modules.

#### 3.2.3.1a Outcome Evaluation

Outcome evaluation is to evaluate whether the psychosocial intervention worked on those who received the ReSHape intervention module. An online Quasi-experimental study will be conducted to evaluate the effectiveness. Standardized tools were utilised to record baseline data are as below:

**Primary Outcomes :** Patient Health Questionnaire (PHQ-9), Generalized Anxiety disorders (GAD-7), health-related quality of life (EQ-5L-5D)

**Secondary Outcomes:** Self-reported weight and height, Psychosocial indicators Resilience Scale 14-items (RS-14) and Health Literacy 12-items, Santa Clara Strength of Religious Faith is a 5items, Poverty Attribution 21-items, Mental Help-Seeking Attitudes Scale (MHSAS) and Self-Stigma of Seeking Help (SSOSH) scale

#### **Others:** Socio-demographic

The data collection was conducted at baseline pre-test (T0), post-test (T1). The details of the instrument for this study have been described in length under methodology for a cross-sectional study.

#### 3.2.4 Sampling

Details of the sampling methods were mentioned above under the **3.7.2** study site and Target **Population**.

#### 3.2.5 Sample size calculation

Based on Mathias et al. (2018) study on the effectiveness of resilience intervention to improve the mental status among young women in India and a local study for the effectiveness of mindfulness among university students, the effect size of the pre-test and post-test intervention were (d=0.42)(Phang, Chiang, et al., 2015). The sample size was calculated using G\*Power version 3.1.9.4, and the estimated sample size was 50 cases in each arm (after inflated with a 20 % reserved rate). The initial required sample size for the entire study was calculated based on a 0.05 precision level and a 95 per cent confidence interval with the power of 80 per cent. Experts in module development have suggested that the validation of the modules is similar to the validation for research instruments (Sidek, 2005). Therefore the sample size for validation of modules was 30 respondents, and a similar sample size was observed in other modules' development studies (Ahmad et al.; Talib et al., 2015)

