## Null hypothesis (H0):

There is no significant difference in the mean differences for the **primary outcomes variables and secondary outcomes variables** among B40 respondents at the community housing project in the intervention compared to the control. **Alternative hypothesis:** There is significant difference between the mean differences of the **primary outcomes variables and secondary outcomes variables** among B40 respondents at the community housing project in the intervention in comparison to the control arm.

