#### 3.2.7.2 Data analysis

The preliminary raw data will be retrieved from REDCap and was organised before it is imported to STATA version 17.0 for statistical analysis. All the data interpretation will be based on the significant level of 0.05 with a power of 80%.

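### Section 3.2.5 claims 80% power with 50 per arm from a pre-test/post-test d of 0.42, but a between-arm test without a baseline gain has about 46–55% power for that effect.

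*Protocol*

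**What the plan says.** Section 3.2.5 takes its effect size from two cited studies, one of a resilience intervention and one of mindfulness, and writes that "the effect size of the pre-test and post-test intervention were (d=0.42". Using G*Power it reports that "the estimated sample size was 50 cases in each arm (after inflated with a 20 % reserved rate"), and that the size was "calculated based on a 0.05 precision level and a 95 per cent confidence interval" "with the power of 80 per cent". It does not name the test, the number of tails, the outcome behind the 0.42, or a correlation between the two time points. Section 3.2.7.2 repeats a "significant level of 0.05 with a power of 80" per cent for all data interpretation.

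The comparison to be tested is between arms:

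- The first Phase 2 null hypothesis in 1.6.2 begins "There is no significant difference in the mean differences for the" primary and secondary outcomes, and sets intervention against control.
- Section 3.2.1 plans a post-test comparison of the two arms.
- The formula under Inferential Analyses subtracts the control arm's pre-post change from the intervention arm's. The chosen models are a repeated-measures mixed model for continuous outcomes and a logistic mixed model for EQ-5D, dichotomised at its median.

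Section 3.2.2.1 restricts entry to PHQ-9 scores of 5 to below 10 and GAD-7 scores of 5 to below 8.

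**The concern.** A pre-test/post-test effect of 0.42 and a between-arm effect of 0.42 need very different sample sizes. A paired comparison has one set of differences; a comparison of two arms carries the sampling error of both. If 0.42 is a change within one group, it also equals the between-arm effect only when the control arm does not change at all, and section 3.2.3.2 gives controls educational modules, pamphlets and a video. A size near 50 that suits a single-group comparison would then be presented as 80% power for a comparison in which it delivers much less. What is at stake is a headline design claim, made twice, that the stated inputs do not support and that readers will use to interpret the effectiveness results.

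**Working it through.** **Inputs.** From 3.2.5: d = 0.42, α = 0.05, power 80%, 50 per arm after 20% inflation. That implies 50 × 0.8 = 40 evaluable per arm if the reserve means division by 0.8, or 50 / 1.2 ≈ 42 if it means multiplication by 1.2. Sidedness is not given; the hypotheses are non-directional, so two-sided is assumed and one-sided is shown as a check. Calculations use the noncentral t distribution.

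**1. Can the plan's 50 be reproduced?** Noncentrality is d√n for a paired test and d√(n/2) for two arms of n.

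| Test at d = 0.42 | n for 80% power | After ×1.2 / after ÷0.8 |
|---|---|---|
| Paired t, two-sided (single group) | 47 | 57 / 59 |
| Paired t, one-sided (single group) | 37 | 45 / 47 |
| Two-sample t, two-sided (per arm) | 90 | 108 / 113 |
| Two-sample t, one-sided (per arm) | 71 | 86 / 89 |

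None gives exactly 50. The nearest matches are single-group tests: a one-sided signed-rank test needs about 39, or 49 after ÷0.8. With 50 pairs a two-sided paired t-test has 83% power, and with 40 it has 74%. No unadjusted two-sample test comes close to 50 per arm.

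A repeated-measures ANOVA interaction with f = 0.21 gives 47 in total at a correlation of 0.5. At a correlation of about 0.15 it gives 39 per arm, or 49 after ÷0.8. But f = 0.21 for a two-by-two interaction means a difference in change of 4 × 0.21 = 0.84 SD, so this route does not give 80% power for a between-arm 0.42 either.

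**2. Between-arm power, no gain from baseline.**

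| Analysed per arm | Two-sided | One-sided |
|---|---|---|
| 40 | 45.8% | 58.6% |
| 42 | 47.7% | 60.4% |
| 50 | 54.8% | 67.0% |
| 90 | 80.0% | 87.7% |

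The effect detectable with 80% power, two-sided, is 0.63 SD with 40 per arm and 0.57 SD with 50.

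**3. Between-arm power when baseline is used.** This applies if 0.42 is in SDs of the raw score. Adjusting for a baseline with correlation r turns the effect into d / √(1 − r²); a change score turns it into d / √(2(1 − r)). Each cell runs from 40 to 50 per arm, two-sided.

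| r | Baseline-adjusted | Change score |
|---|---|---|
| 0.3 | 49–59% | 35–42% |
| 0.5 | 57–67% | 46–55% |
| 0.7 | 74–83% | 67–77% |
| 0.75 | 80–88% | 75–84% |
| 0.8 | 87–93% | 83–91% |

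The correlation at which adjusted power reaches 80% is r = √(1 − (0.42/0.634)²) ≈ 0.75 with 40 per arm and √(1 − (0.42/0.566)²) ≈ 0.67 with 50.

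If 0.42 is instead in SDs of change, the difference-in-change test has the 46–55% of step 2, taking no change in controls. Any improvement in controls lowers it.

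**The case against.** The strongest reply is that the planned analysis is a repeated-measures model on both time points, not an unadjusted t-test. If 0.42 is in raw-score SDs, the baseline carries information, and with a correlation of about 0.7–0.75 the study would reach 80%. This stands as a condition: 46–55% is the power without such a gain and must be labelled so. It does not rescue the claim, because the protocol gives no correlation. Restricting entry to narrow bands of PHQ-9 and GAD-7 also normally lowers the correlation of those scores with follow-up. A reader might go further and say that adjustment recovers little; that would rest on assumed score distributions that are not in the protocol.

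Second, the origin of 0.42 cannot be confirmed. The wording may describe a within-group change or an effect from studies with a pre/post design. So it cannot be asserted that a paired calculation produced the 50, only that the calculation is not identified and that no unadjusted two-arm test reproduces it.

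Third, section 3.2 labels this a feasibility study focused on acceptability and practicality. That is fair, and it is why no larger sample is asked for. But Objective 5 and 3.2.3.1a also set out to evaluate effectiveness, 1.6.2 states formal hypotheses, and the 80% figure is stated outright.

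A reader might also infer that controls will make half the gain, which would cut power to about 15% with 40 per arm, or that a null result will be taken as proof of no benefit. The protocol supports neither; the first is an arbitrary assumption and the second a prediction.

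**Conclusion.** The point holds in conditional form. The 80% power in 3.2.5 and 3.2.7.2 is not supported by the stated inputs for the between-arm comparison that the trial tests. Without a gain from baseline, two-sided at 5%, power for a between-arm 0.42 is about 46% with 40 completers per arm and 55% with all 50; 80% would need 90 per arm before dropout. A one-sided test still falls short, at 59–67%. With baseline adjustment and 0.42 in raw-score SDs, 80% needs a correlation of roughly 0.7–0.75, unstated and less likely for PHQ-9 and GAD-7 given the entry limits. It would be too strong to read 46–55% as the unconditional power of the planned model. The figures concern the continuous outcomes PHQ-9 and GAD-7; a standardised mean difference does not describe the dichotomised EQ-5D.

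**What to change.** Keep 50 per arm and reword.

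- In 3.2.5, name the comparison, the test and its sidedness. State that for PHQ-9 and GAD-7, with 50 enrolled and 40 completing per arm, two-sided 5% and no gain from baseline correlation, the study has 80% power for a between-arm standardised difference of 0.63 and about 46% for 0.42.
- Add power over a range of assumed correlations, such as the table above, marked as assumptions.
- Say that these figures do not apply to the dichotomised EQ-5D.
- Delete the 80% power claim in 3.2.5 and 3.2.7.2.
- Present effectiveness as preliminary between-arm estimates with 95% confidence intervals, in keeping with the feasibility label.

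The cost is text in two sections and a less favourable stated power. No participants are added, and enrolment and the planned models do not change.

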#### 3.2.6 Study Instruments

The baseline data from the intervention study and post-intervention qualitative study will be collected using the same instrument that was described under cross-sectional study . All the tools will be converted to an online survey in REDCap, and a pre-test was done before the actual data collection.

ReSHape Modules and the module activities evaluation form were created based on the objectives described under **sub-heading 3.1.** and the validation outcomes were presented in the subsequent sub-heading.

# 3.2.6.1 Sociodemographic Questionnaires

Sociodemographic questionnaires captured the background information of the respondents, which include the items stated below

- a) Individual characteristics: age, gender, ethnicity and marital status.
- b) Household information: years lived in the area, size of household
- c) Socioeconomic status: education level, pre and post-covid monthly household income and employment status, ownership of assets (example: cash, car, houses, etc), ownership of communication tools.
- d) Social capital: frequencies of interaction with the community

# 3.2.6.2 Health-related history Questionnaires

Health related history section captured the substance used, previous stressful life event, weight (Kg) and height (m) of the respondents.

The participants administered substance usage checklists to assess if the respondents took any non-prescribed substances from the most typical substances list, such as tobacco, alcohol, cannabis, cocaine, amphetamine-type stimulant inhalant, sleeping pills, hallucinogens, opioids and other substances. Respondents have to answer "yes" or "No" if they have ever taken these substances.

The stressful life event checklist was constructed based on a literature review (Maideen et al., 2015; Rosmalen et al., 2012). Respondents were required to answer "yes" or "no" to the events they perceived as a major events that caused emotional distress to them in their lifetime. A face validation was performed for this list with a panel of experts comprised of psychiatrists, family physicians, and public health specialists from the investigator's Master of Public Health (MPH) mental health study among the preschool caregivers ([name], 2019) History of assault, loss of loved one, abuse during childhood, severe marital problems, severe family problems, serious injury or accidents are the events that were inquired about in the questionnaire. Respondents who answered "yes" to any life events will take as positive for life events in the binary category

Presence of Chronic Diseases. Diseases were self-reported by the participants based on the diagnosis by medical professionals. Chronic diseases are conditions that last one year or more and require ongoing medical attention or limit activities of daily living, or both (CDC, 2021). Some items included chronic illnesses list are hypertension, diabetes mellitus, heart diseases, stroke, mental illness, cancer, etc. Respondents have to indicate "yes" if they have a particular chronic illness. Any "yes" to the item will prompt the enumerator to cross-check with the respondents' home-based treatment card. They will be guided with a list of chronic diseases adopted from PARTNER's study protocol (Appendix G).

#### 3.2.6.3 Patient Health Questionnaire 9 items (PHQ 9)

The Patient Health Questionnaire 9-item (PHQ-9) is a Diagnostic and Statistical Manual of Mental Disorders, Fourth Edition (DSM-IV) based instrument designed to identify recent symptoms associated with major depression during the past two weeks. It is a subset of the PRIME-MD diagnostic instrument for common mental health disorders. This is a widely used free of charge tool that has been translated to various languages and tested in various populations (Teymoori et al., 2020). The original English version of the instrument was validated by Kroenke et al. among clinical settings respondents with good internal reliability. PHQ-9 consists of 9 items with four points scales, with each item scored from 0–3 and an overall range score of 0–27. The scores have been further classified according to the severity of depressive symptoms: increasing severity: minimal (0-4), mild (5-9), moderate (10-14), severe (15-19), and very severe (20 or greater). This is a practical tool for intervening depression, as each severity level of the scoring was given the possible intervention in the PRIME-MD (Kroenke et al., 2001).

This study adopted the total scoring methods to identify depression instead of algorithm scoring methods, as the former has better diagnostic performance (Manea et al., 2015). The scoring classification mentioned above was used, and in the present study, the cut-off point of  $\geq$  5 indicates the presence of mild to severe symptoms of depression and scores of  $\geq$  10 indicates moderate to very severe depression that requires referral for further clinical assessment. This cut-off was used in the final inferential statistic analysis, selection of the feasibility study subjects and cases for referrals

The Malay and English version of PHQ-9 was validated in Malaysia, with results showing good internal validity (Cronbach's  $\alpha = .70$ ) (M. S. Sherina et al., 2012). The Malay version was used in conducting a large local community and national level research in this country(IPH, 2019b; Kader Maideen et al., 2014).

#### 3.2.6.4 Generalised Anxiety disorders (GAD-7)

Anxiety scale 7-item (GAD-7) is also part of the PRIME-MD diagnostic instrument based on DSM-IV construct for generalised disorders. This instrument inquires about the anxiety symptoms of the respondents for two weeks duration. The English version of GAD-7 was first validated by [name] et al. (2006) among the adult patients at the primary care settings with the excellent internal consistency of (Cronbach's  $\alpha = 0.92$ ), and Test-retest reliability was also good (intraclass correlation=0.83). This is a seven items instrument with four points rating scales with the scoring system of 0 = "not at all", one = "several days", two = "more than half the days", and three = "nearly every day". The total score ranged from 0 to 21. The score has been classified into five intervals of severity in the order of minimal (0-4), mild (5-9), moderate (10 -15) and severe (16-21)(Spitzer et al., 2006).

Using the total scoring method, two-level cut-off points will be utilised for the bivariate analysis of the cross-sectional study,  $\geq 5$  for mild to severe anxiety disorders and  $\geq 8$  for probable anxiety disorders, which require a referral for clinical assessment. This cut-off was used in the final inferential statistic analysis, selection of the feasibility study subjects and cases for referrals

The Malay version was validated by Sherina et al.; results showed good internal reliability (Cronbach's  $\alpha = .74$ ) (Sidik et al., 2012). GAD-7 was also tested in one large prevalence study in Selangor and a national level survey (Kader Maideen et al., 2015).

#### 3.2.6.5 European Health-Related Quality of Life, EQ-5D-5L

EQ-5D-5L is a standardised measure of Health-Related Quality of Life (HRQoL) developed by the Euro-Qol Group to provide a simple, generic questionnaire for clinical

and economic appraisal or population health status surveys. The EQ-5D-5L is part of the EQ-5D family of instruments.

EQ-5D-5L comprised the descriptive system (EQ-5D) and a visual analogue scale (EQ-VAS) that required a few minutes to complete.

The descriptive system is divided into five dimensions, providing information on the respondent's perceptions of their health status, including mobility, self-care, usual activities, pain or discomfort, and anxiety or depression. Each dimension is rated based on five response levels which include 1 = no problems, 2 = slight problems, 3 = moderateproblems, 4 = severe problems or 5 = unable to/extreme problems(Oemar & Janssen,2013).

For instance, if a respondent scored 12345 for the mobility domain, the interpretation is no problems with mobility, slight problems with self-care (washing or dressing), moderate problems with doing usual activities, severe pain or discomfort and extreme anxiety or depression. Each health state can potentially be assigned a summary index score based on societal preference weights for the health state. This health state index scores generally range from less than 0 (where 0 is the value of a health state equivalent to dead; negative values representing values as worse than dead) to 1 (the value of full health), with higher scores indicating higher health utility(Oemar & Janssen, 2013). Each country has its own standardised value set, generated through a local study. The value set for Malaysia was published by Shafie, Vasan Thakumar, Lim, Luo, et al. (2018).

Visual analogue scale (EQ-VAS) records the respondent's overall current health on a vertical visual analogue scale, where the endpoints are labelled 'The best health you can imagine and 'The worst health you can imagine. The EQ-VAS provides a quantitative measure of the patient's perception of their overall health. The respondents need to mark on a scale ranging from 0 to 100.

This tool has been utilised worldwide with multi-language translation (Cheng et al., 2021). It was also tested in the bottom 40% of the income group through a local social welfare registry E-kasih involving the low-income households, people with disabilities and the aborigines in Malaysia (Wan Puteh et al., 2019). As the B40 population has variations in literacy level, the brevity of the tool helps them answer the question effortlessly. A Malay version of EQ-5D-5L has been selected because it is the national language and has acceptable reliability (Shafie, Vasan Thakumar, Lim, Luo, et al., 2018). Another study targeted clinical cases showed excellent Cronbach's alpha (0.85) for five dimensions of the descriptive system. (Tran, Ohinmaa, & Nguyen, 2012).

